10.7. Physical Examination

Physical examinations results will be displayed in by subject listings. No summary tables of physical examination are planned.

10.8. Prior and Concomitant Medications

Prior and concomitant medication verbatim terms captured via the EDC system will be mapped to Anatomical/Therapeutic/Chemical (ATC) class and Preferred Names using the most current versions of the World Health Organization (WHO) Drug Dictionary Enhanced available.

Prior and concomitant medications will be summarized separately by WHO ATC class and preferred name. Medications with a start date prior to first dose will be considered prior medications. Medications with a start date on or after first dose date will be considered concomitant medications. Medications with a start date prior to first dose date and an end date on or after first dose or that are ongoing will be considered as prior medications. These summaries will present the number and percent of subjects using each medication. Subjects may have more than one medication per ATC class and preferred name. At each level of subject summarization, a subject is counted once if one or more medications at that level is reported for the subject. Each summary will be ordered by descending order of incidence of ATC class and preferred term.

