- b. Subjects are to be scheduled in 21-day intervals (+/- 4 days) after each treatment for subjects in Cohort 2. The next Treatment Visit is to be scheduled 21 (+/- 4 days) after the last treatment, but only after any LSR has resolved sufficiently to allow evaluation of the treatment site. The research team should be in contact with the patient until LSRs are resolved and a treatment visit can be scheduled within 21 days (+/- 4) when possible. The 24-hour phone contact may be conducted at +/- 6 hours. The 7-day phone contact may be conducted +/- 24 hrs.
- c. A final in person safety assessment, ERT, photos and study completion form will be completed at the Day 147 (EOS) Visit for all subjects. EOS conducted outside the Day 147 EOS visit window will be considered a protocol deviation. Treatments may be administered up to Day 75 in Cohort 2. Subjects in Cohort 2 are to attend all visits whether they have achieved complete clearance prior to and at the Day 84 (- 0/+ 8 days) EOT assessment.
- d. Demographics: date of birth, sex, race/ethnicity will be collected.
- e. Vital signs (e.g., temperature & heart rate) will be obtained at each treatment prior to application of Study drug. Height and weight will be collected at Screening/Day 1, EOT Day 84 (- 0/+ 8 days) and subsequent follow up visits Day 105, 126 and 147 (EOS).
- f. Limited physical examination. Symptom or AE-directed physical examination may be performed if warranted. (See Source/eCRF for a more detailed description)
- g. Dermatologic exam including Fitzpatrick Skin Type, location of each wart is identified and documented on the body map and source as outlined in the MOP. Measurements of warts should be recorded on Day 1 prior to treatment to confirm they meet inclusion criteria of ≤ 10 mm in diameter and ≤3 mm in height. Wart location, measurements and assessments are to be completed prior to each treatment application and/or each in-person visit. New warts should be recorded in the corresponding Source/eCRF. Instructions for measuring and documenting the and measurements are provided in the Manual of Operations.
- h. Paring at first visit by Dermatologist or qualified designee. Paring at additional treatment visits if significant hyperkeratosis or at Investigator’s discretion.

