4.2.2 Exclusion Criteria

Candidates will be excluded from the study if they:

1. Are unable to cooperate with the requirements or visits of the study, as determined by the investigator.
2. Are systemically immunosuppressed or have required, or will require, systemic immunosuppressive or immunomodulatory medication (including oral or parenteral corticosteroids) within 30 days prior to enrollment or during the course of the study. (Routine use of inhaled or intranasal corticosteroids during the study is allowed.)
3. Have any chronic or acute medical condition that in the opinion of the investigator, may interfere with the study results or place the subject at undue risk. (e.g., human immunodeficiency virus, systemic lupus erythematosus, viral hepatitis, uncontrolled diabetes). NOTE: Immunizations and flu shots may be administered throughout the study, but not within 5 days before or after treatment.
4. Have more than 6 common warts at baseline.
5. Present with any verruca plana, mosaiform, filiform, subungual (under the nail), genital or anal warts. In Cohort 2, subjects with periungual warts are also excluded.
6. Have any warts present at baseline in an anatomic location the subject, parent/guardian or the physician is unwilling to treat or are located in an area that cannot be easily occluded tape.
7. Have had any previous treatment of common warts including but not limited to the use of cantharidin, antivirals, retinoids, salicylic acid, lactic acid, hydrogen peroxide, candida antigen, diphencyprone, dinitrochlorobenzene, sandalwood oil, thuja oil, squaric acid dibutyl ester, povidone iodine, curettage or freezing of warts in the past 14 days. In addition, these treatments or any other over-the-counter wart treatment should not be implemented during the course of the study.

8. Have been treated within 14 days with a product that contains cantharidin (topical or homeopathic preparations) for any reason prior to screening.
9. Have received another investigational product as part of a clinical study within 30 days prior to the first application of the Study drug.
10. Currently have, or have a history of, epidermodysplasia verruciformis.
11. Have a history of illness or any dermatologic disorder which, in the opinion of the investigator, will interfere with accurate assessment of the warts or increase the risk of adverse events.
12. Have an active malignancy or are undergoing treatment for any malignancy.

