5.4 Concomitant Medications

All medications taken within 14 days prior to the first dose of the Study drug will be classified as prior medication; while all medications used after the first dose of Study drug will be classified as concomitant medications. Prior and concomitant medications will be recorded in the eCRF, along with the reasons for administration and durations of use.

Subjects who have had previous treatment of common warts, including but not limited to, cantharidin, antivirals, retinoids, salicylic acid, lactic acid, hydrogen peroxide, candida antigen, diphencyprone, dinitrochlorobenzene, sandalwood oil, topical or homeopathic remedies containing cantharidin, thuja oil, squaric acid dibutyl ester, povidone iodine,

curettage or freezing of warts within 14 days prior to screening should not be enrolled for at least 14 days. In addition, these treatments or any other over-the-counter wart treatment should not be implemented during the course of the study.

Subjects that have participated in another clinical trial utilizing an investigational product may be enrolled within 30 days prior to the first application of the Study drug.

Medications or treatments that can interfere with the evaluation of the Study drug [e.g., topical steroids, PDE-4 inhibitors (such as Eucrisa®), and calcineurin inhibitors (pimecrolimus, tacrolimus)] should not be used on the day of treatment and should not be applied within 5cm of treated skin lesions. Particular attention will be paid to treatments that can influence the intended effects or mask the side effects of the Study drug (e.g., topical steroids). Lotions and creams such as sunscreens should not be used for a minimum of 4 hours before treatment and should not be applied within 5cm or on treated skin for 24 hours following treatment. Immunizations and flu shots may be administered throughout the study but not within 5 days before or after treatment.

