AEs may include pre-treatment or post-treatment events that occur as a result of protocol-mandated procedures (e.g., invasive procedures, modification of the subject's previous therapeutic regimen). AEs should be captured even if they occur during periods without drug treatment or post-treatment periods. AE collection begins once the subject has signed informed consent and will continue until the EOS visit has been completed.

The investigator is responsible for performing periodic and special assessments for AEs. The investigator and study personnel will note all AEs mentioned by the subject starting from the day the informed consent is signed until the end of study visit (EOS; Day 84). All clinical complaints volunteered by or elicited from the subject or parent/guardian during the study will be recorded on the appropriate page of the source and eCRF for the study period indicated. The subject will receive appropriate treatment and medical supervision for any AE that occurs.

All unresolved AEs will be followed until the condition resolves and/or stabilize, the subject is lost to follow-up or 30-days after the end of study (EOS visit or up to 30 days after the EOS visit, whichever comes first.) All AEs will be summarized in the annual report or more frequently if requested by the regulatory agency. SAEs require special reporting in addition to documentation in the eCRF as described in Section 7.3.

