2.2. Study Objectives

2.2.1. Primary Objectives

The primary objectives for Cohort 2 are (1) to evaluate the efficacy of dermal application of VP-102 when applied once every 21 days for up to 4 applications to common warts on subjects 12 years and older by assessing the proportion of subjects achieving complete clearance of all treatable warts at the EOT Visit (Day 84) and (2) to assess the safety and tolerability of VP-102 applied to common warts by assessing adverse events including expected local skin reactions, physical examinations, and concomitant medications.

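### SAP 10.8 classes medications continuing past first dose as prior, contrary to Protocol 5.4, so the Cohort 2 concomitant-medication table omits them; separately, Protocol 7.1 dates EOS for AE recording at Day 84 for both cohorts

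*SAP*

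**What the plan says.** **Medications.** SAP 10.8 classifies by start date. A start before first dose makes a medication prior. For the other class, "Medications with a start date on or after first dose date will be considered concomitant medications". It then settles the overlapping case expressly: a medication begun before first dose with "an end date on or after first dose or that are ongoing will be considered as prior medications". The two classes go into separate summary tables. Protocol 5.4 classifies by use instead. Anything taken in the 14 days before first dose is prior, and "all medications used after the first dose of Study drug will be classified as concomitant medications". The SAP covers Cohort 2 only.

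**End of study for adverse events.** Protocol 7.1 has sites note AEs "starting from the day the informed consent is signed until the end of study visit (EOS; Day 84", with no cohort named. For Cohort 2, footnote c of Protocol Table 2 says the "study completion form will be completed at the Day 147 (EOS) Visit for all subjects". Footnotes e, j and p of that table and Protocol 4.1 also call Day 147 EOS. Table 2 schedules AE collection at the Day 105, 126 and 147 visits, and SAP 7.1 counts a subject as completing the study only with a Day 147 visit. Protocol 9.2.4 and SAP 10.2 keep AEs with onset after EOS out of the summary tables, though not the listings. Neither section says which day EOS is.

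**The concern.** The Cohort 2 primary safety objective in SAP 2.2.1 is to be assessed through "adverse events including expected local skin reactions, physical examinations, and concomitant medications". A table headed concomitant medications should therefore show what subjects were taking while on study. Under SAP 10.8 it shows only what they started while on study. A drug begun the day before first dose and taken throughout is left out; the same drug begun on Day 1 is counted.

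Protocol 5.4 also commits to more than bookkeeping: "Particular attention will be paid to treatments that can influence the intended effects or mask the side effects of the Study drug", with topical steroids as its example. Protocol 4.2.2 adds that "Routine use of inhaled or intranasal corticosteroids during the study is allowed". Medications of either kind that a subject is already using at Day 1 are the ones the SAP rule removes.

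For adverse events, the unlabelled Day 84 in Protocol 7.1 leaves room for sites to stop recording, or programmers to stop tabulating, at different times in Cohort 2.

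**Working it through.** **1. The two medication rules applied to each type of record**

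No figure in the plan needs reproducing; this is a comparison of rules.

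| Medication record | SAP 10.8 | Protocol 5.4 |
|---|---|---|
| Started and ended before first dose | Prior | Prior, if taken in the preceding 14 days |
| Started before first dose, ended on the day of first dose | Prior | Unclear whether this is use after first dose |
| Started before first dose, ended later or ongoing | Prior | Concomitant (also prior, if taken in the preceding 14 days) |
| Started on or after first dose | Concomitant | Concomitant |

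The third row is a plain contradiction. SAP 10.8 does not use the word *only*, but its concomitant definition requires a start on or after first dose and it tabulates the classes separately, so a third-row record cannot reach the concomitant table. The second row is a boundary case on which the conclusion does not depend.

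The documents do not say how many of the approximately 35 Cohort 2 subjects will have such a record, so the size of the omission cannot be calculated.

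**2. Where EOS falls for Cohort 2 adverse events**

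Inputs: Day 84 (Protocol 7.1); Day 147 (Protocol Table 2 footnotes, Protocol 4.1, SAP 7.1); a limit of 30 days after EOS for following unresolved AEs (Protocol 7.1 and 7.8).

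Share of the 147 days lying after EOS, and so outside the AE tables:
- EOS = Day 84: (147 − 84)/147 = 63/147 = 42.9%.
- EOS = Day 147: (147 − 147)/147 = 0%.

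Latest day for following an unresolved AE:
- EOS = Day 84: 84 + 30 = Day 114, before the Day 126 and Day 147 visits.
- EOS = Day 147: 147 + 30 = Day 177.

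Most Cohort 2 text supports Day 147. The paragraph of Protocol 7.1 just before the one quoted runs AE collection to completion of the EOS visit without giving a day. The Day 84 label is correct for Cohort 1; the defect is that it is not limited to Cohort 1.

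**The case against.** **On medications.** No record is lost: continuing drugs appear in the prior table and the listings, and those taken in the 14 days before first dose are prior under the protocol as well. The SAP states its rule openly, the analysis is descriptive, and no efficacy endpoint or population is shown to depend on this table. Wart treatments are barred in the 14 days before screening and during the study, so in a compliant subject any such therapy, or a drug newly started for an AE, begins after first dose and is counted. The protocol's remark about masking side effects follows a list of topical agents; nowhere does it say that inhaled or intranasal steroids mask anything.

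All of this is right, and it limits the weight of the point. It does not remove the contradiction. The prior table will mix drugs stopped before Day 1 with drugs taken throughout, so neither table shows how many subjects used a given drug during the study; a reader would have to rebuild that from listings. The omission follows from the rule whether or not a particular drug masks effects.

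**On EOS.** This is a separate matter and should not add weight to the first. The SAP lists EOS and EOT as separate abbreviations, uses EOT for Day 84 and ties completion to Day 147, so Day 147 is the natural reading of SAP 10.2. Treatment ends by Day 75 unless the sponsor approves otherwise, so 43% of days is not 43% of AE information. Table 2 schedules AE assessment at every follow-up visit. These points stand, and they make the 43% and Day 114 figures the consequence of the less likely reading. What remains is that Protocol 7.1 gives sites a different date, and that the sections applying the cut-off give none.

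**Conclusion.** The main point holds: SAP 10.8 contradicts Protocol 5.4, nothing in either document reconciles them, and the Cohort 2 concomitant-medication table produced under the SAP will omit every medication already in use at first dose and continued. The effect is confined to that table. Its size is unknown, because the number of continuing medications is not given. The change should be made because the table serves a primary objective, but no efficacy result turns on it.

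The EOS point also holds, as a lesser inconsistency. The practical effect is nil if everyone reads Cohort 2 EOS as Day 147, and up to 63 of 147 days outside the AE tables if someone applies the date in Protocol 7.1.

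**What to change.** - **SAP 10.8:** replace the sentence on overlapping medications so that one started before first dose and continuing on or after it is concomitant, in line with Protocol 5.4. It may be shown in the prior table as well. Wording this by date also settles the case of a drug ending on the day of first dose.
- **Protocol 7.1 and 9.2.4:** state EOS by cohort, Day 84 for Cohort 1 and Day 147 for Cohort 2.
- **SAP 10.2:** define EOS as Day 147 for Cohort 2.
- **Same edit, for consistency:** Protocol 4.1 (the Cohort 2 paragraph on the Day 84 window), 4.3.1, 8.1 and 9.2.7 also pair end of study with Day 84. In 4.1 and 9.2.7 the Cohort 2 visit meant is the EOT visit, so those should be relabelled EOT and not moved to Day 147; the primary endpoint stays at Day 84.

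The cost is one SAP sentence, one SAP definition and a wording clarification in the protocol. No new data are needed, because Table 2 already schedules both AE and concomitant-medication collection at the follow-up visits.
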